4.2 Protocol changes during the study

The trial started out with revision B (Approval December 9th, 2014) of the clinical investigation plan. On March 30th, 2015 CIP Rev. C was approved with change from a paper-based Case Report Form to an electronic CRF. Rev. D resulted from an additional study center (change from monocenter to multicenter study) and from previous experiences within the trial (Approval August 5th, 2015). This clinical trial was finished with CIP Rev. E approved on April 13th, 2016. The most important changes to the protocol were as follows:

 Implantata Ophthalmic Products GmbH	Clinical Investigation Report ARGOS-KP01	Revision A Page 44 of 114
--	---	----------------------------------

CIP Rev. D: Changes in Determination of ARGOS-IO Implant Size

CIP 8.4.4.9, p. 68 “Anterior eye segment measurement, Optical Biometry”

- “If optical biometry is not possible, for example due to opacity of the subject’s cornea, ultrasound biomicroscopy or corneal diameter measurement using an ophthalmosurgical caliper will be used to assess the dimension of the subject’s anterior chamber.”

This method has been shown to be a feasible approach during the first implantation by [name].

CIP Rev. E: Changes in Sample Size Considerations and Usage of the ARGOS-IO injector during implantation (optional)

CIP Synopsis, p. 6 “Sample Size Considerations”, CIP 8.3.7, p. 68 “Number of subjects required”, CIP 8.38, p. 68 “Estimated time needed to select the planned number of subjects” and CIP 9.2, p. 83 “Sample Size Calculation”

- The enrollment from a minimum of 6 and a maximum of 10 patients was increased to a minimum of **10** and a maximum of **15** patients. Due to very different baseline parameters of the patients and a good tolerance of the ARGOS-IO implant until then, the enrollment number was increased to gain more experience.

CIP 4.7, p. 35 “Description of any specific medical or surgical procedures involved in the use of the investigational device”, CIP 5.1.1.3, p. 38 “Sterilization Verification”, CIP 6.5, p. 54 “Possible Interactions with concomitant Medical Treatments” and CIP 8.4.5.2, p. 75 “ARGOS-IO pressure sensor implantation”

- The surgeons was given the option to use the ARGOS-IO Implant Injector as in the ARGOS-02 study for an easier access to the posterior chamber by an intact narrow pupil.

In the following table is listed which Revision of the Clinical Investigation Plan was valid for.

Toxic epidermal necrolysis	1	7.7
Surgical and Medical Procedures		7
Eye operation	3	23.1
Keratoplasty	3	23.1
Photocoagulation	2	15.4
Trabeculectomy	2	15.4
Amniotic membrane graft	1	7.7
Cataract operation	1	7.7
Corneal transplant	1	7.7
Phacocystectomy	1	7.7

Source: Final Statistical Output – Tables

Table 14.1.4.2.1 – Disease Characteristics concerning Study Eye

Table 14.1.4.7.1 – IOP Measurements at Screening Visit

Table 14.1.5.2.1 – Medical History Related to Study Eye by SOC and PT

Table 14.1.5.4.1 – Concomitant Diseases Related to Study Eye by SOC and PT

%: Percentage based on N

n: Number of subjects with data available

N: Number of subjects in total (Safety Set)

(*): Previously or currently treated

n¹: Number of patients reporting at least one past diagnosis/procedure

Table 6: Summary of Concomitant Diseases without any Relation to Study Eye

Concomitant diseases	Total (N=13)	
	n¹	%
Any System Organ Class	12	92.3
Blood and Lymphatic System Disorders	1	7.7
Anaemia	1	7.7
Congenital, Familial and Genetic Disorders	1	7.7
Cataract congenital	1	7.7
Endocrine Disorders	5	38.5
Hypothyroidism	4	30.8
Cushing's syndrome	1	7.7
Eye Disorders	2	15.4
Atrophy of globe	2	15.4
Conjunctivalisation	1	7.7
Macular edema	1	7.7
Retinal detachment	1	7.7
Gastrointestinal Disorders	1	7.7
Hyperchlorhydria	1	7.7
Pancreatic failure	1	7.7
General Disorders and Administration Site Conditions	1	7.7
Pain	1	7.7
Metabolism and Nutrition Disorders	2	15.4
Diabetes Mellitus	2	15.4
Vitamin B12 Deficiency	1	7.7
Neoplasms Benign, Malignant and Unspecified	1	7.7
Leukaemia	1	7.7
Nervous System Disorders	1	7.7
Epilepsy	1	7.7
Psychiatric Disorders	1	7.7
Psychotic disorder	1	7.7
Renal Failure and Urinary Disorders	1	7.7
Renal failure	1	7.7

 Implantata Ophthalmic Products GmbH	Clinical Investigation Report ARGOS-KP01	Revision A
		Page 50 of 114

Respiratory, Thoracic and Mediastinal Disorders	1	7.7
Asthma	1	7.7
Skin and Subcutaneous Tissue Disorders	1	7.7
Dermatitis atopic	1	7.7
Surgical and Medical Procedures	1	7.7
Intraocular lens implant	1	7.7
Vascular Disorders	2	15.4
Hypertension	2	15.4

Source: Final Statistical Output – Tables
Table 14.1.5.3.1 – Concomitant Diseases by SOC and PT

#: Percentage based on N
 N: Number of subjects in total (Safety Set)
 n¹: Number of patients reporting at least one past diagnosis/procedure

4.5 CIP Compliance

A summary of the protocol deviations is given by Table 8.

Table 8: Summary of Protocol Deviations

Parameter	Total (N=13)	
	n	%
At least one deviation	12	92.3
Deviation related to		
Patient rights/welfare	0	0.0
Patient safety	1	7.7
Integrity of research data	0	0.0
Other	11	84.6
Involvement of deviation		
Consent process	1	7.7
Patient eligibility	0	0.0
AE/SAE reporting	0	0.0
Assessments	10	76.9
Device implantation	0	0.0
Visit window/missed visit	12	92.3
Audit finding that require corrective action	0	0.0
Other	4	30.8
Source: Final Statistical Output – Tables Table 14.1.3 – Summary of Protocol Deviations		
%: Percentage based on N N: Number of subjects in total (Treated patients)		

Patient rights and welfare were not affected by the protocol deviations. The deviation related to the patient safety was a missed signature on the Informed Consent Form by the investigator. For this issue, the investigator stated with actual date that the patient was informed about the study, agreed to participate, signed and got a copy of the patient information and Informed Consent Form.

Most protocol deviations include visits out of the time window and assessments which were not completed as described in the CIP. The most frequent violation of the assessments was missing the external eye photography. This was only a minor deviation because these photos were not included in the evaluation. Missed surgical manometries were not performed due to medical reasons (hypotony of eye, Site DE-02 did no further surgical manometry in aniridia patients after SAEs (see *4.8.1.1 Serious Adverse Events in the follow-up period*)).

 Implantata Ophthalmic Products GmbH	Clinical Investigation Report ARGOS-KP01	Revision A Page 53 of 114
--	---	----------------------------------

4.6 Data Sets Analyzed

Safety Population

The safety population comprises all subjects for whom ARGOS-IO pressure sensor implantation was attempted, defined as introduction of the ARGOS-IO pressure sensor into the eye, whether or not the implantation was successful.

The Per-Protocol-Set (PPS) population

The Per Protocol Set (PPS) will comprise all subjects in whom ARGOS-IO pressure sensor was successfully implanted and for whom the full data set including IOP measurements made in the clinic and safety data according to protocol are available until 28 weeks (Visit 11) after surgery. Because IOP measurements conducted outside the clinic will made at varying times under varying conditions, they are not anticipated to be comparable to those made in the clinic and will not be included in the Per-Protocol evaluation of agreement.

Additional information about the drop-outs: all subjects who revoke their consent and agreement preoperatively will be regarded as screen failures and will not be included in the statistical evaluation. All subjects who revoke their consent and agreement postoperatively will be considered withdrawals. Unless the subject also withdrew consent to use their data, they will be evaluated in the safety analysis.

[figure not shown]
4.7 Performance

4.7.1 Tonometry

4.7.1.1 ARGOS-IO System

Telemetric IOP assessments by the ARGOS-IO implant was conducted at every study visit of every patient.

In the following line graphs (Figure 6) display the individual ARGOS-IO measurements over per patient at scheduled visits. Post-operative study visits were at Day 1, 5, 10, 15 and week 4, 10, 16, 22, 28, 34, 40, 46 and 52.

Figure 6. Individual IOP follow-up during study period per patient measured with the ARGOS-IO system

IOP Implandata Ophthalmic Products GmbH	Clinical Investigation Report ARGOS-KP01	Revision A
		Page 68 of 114

4.7.2 User acceptance of the ARGOS-IO system at home by evaluation of patient acceptance questionnaire

[figure not shown]
In all patients who completed the patient acceptance questionnaire was a very high overall acceptance in using the ARGOS-IO system in their daily routine. The instruction for use for the Mesograph reader device was easily to understand, the implant did not cause them any problems and the patients were less concerned about unidentified high IOP.

Patients could give an estimate on a scale of 1 to 7 how strongly they agree with the following questions. 1 means totally disagree and 7 stands for totally agree.

Q2 - To what extend do you agree with the following statements:

[figure not shown]
Based on my experience with the ARGOS-IO system in this study, I would seriously consider

...permanently using ARGOS-IO system at home.

[figure not shown]
Answer	Frequency (N=6)	
	n	%
Completely agree	6	100.0

...using ARGOS-IO system at workplace.

[figure not shown]
Answer	Frequency (N=6)	
	n	%
Completely disagree	1	16.7
Somewhat agree	1	16.7
Completely agree	2	33.3
Missing	2	33.3

...using the ARGOS-IO system while travelling.

[figure not shown]
Answer	Frequency (N=6)	
	n	%
Strongly agree	1	16.7
Completely agree	5	83.3

...recommending the ARGOS-IO system to other glaucoma patients.

Answer	Frequency (N=6)	
	n	%
Somewhat disagree	1	16.7
Indifferent	2	33.3
Strongly agree	1	16.7
Completely agree	2	33.3

[figure not shown]
Q3 – How do you normally have your IOP measured (outside of the study)?

Answer	Frequency (N=6)	
	n	%
Monthly	4	66.7
Every 2 months	1	16.7
Every 3 months	1	16.7

[figure not shown]
Q4 – To what extend do you agree with the following statements regarding the user instructions

...user instructions for the Mesograph reader device can easily be understood.

Answer	Frequency (N=6)	
	n	%
Indifferent	1	16.7
Strongly agree	2	33.3
Completely agree	2	33.3
Missing	1	16.7

[figure not shown]
...user instructions for the Multiline connector can easily be understood.

Answer	Frequency (N=6)	
	n	%
Indifferent	1	16.7
Strongly agree	1	16.7
Completely agree	1	16.7
Missing	3	50.0

[figure not shown]
Q5 – To what extend do you agree with the following statements about the Mesograph reader device?

The Mesograph reader device fits well in the hand...

[figure not shown]
Answer	Frequency (N=6)	
	n	%
Somewhat agree	1	16.7
Strongly agree	1	16.7
Completely agree	4	66.7

The display of the Mesograph reader is large enough...

Answer	Frequency (N=6)	
	n	%
Strongly agree	3	50.0
Completely agree	3	50.0

[figure not shown]
The battery of the MESOGRAPH reader lasts long and can be easily exchanged...

Answer	Frequency (N=6)	
	n	%
Indifferent	1	16.7
Strongly agree	2	33.3
Completely agree	2	33.3
Missing	1	16.7

[figure not shown]
Q6 – To what extend do you agree with the following statements about the implant:

The implant does not cause me any problems...

[figure not shown]
Answer	Frequency (N=6)	
	n	%
Strongly agree	1	16.7
Completely agree	5	83.3

I feel the implant as a foreign body...

Answer	Frequency (N=6)	
	n	%
Completely disagree	4	66.7
Strongly disagree	2	33.3

[figure not shown]
The implant affects my visual field...

Answer	Frequency (N=6)	
	n	%
Completely disagree	6	100.0

[figure not shown]
Q7 – To what extend do you agree the following statements:

Pressure measurements at home do not disturb my daily routine...

[figure not shown]
Answer	Frequency (N=6)	
	n	%
Completely disagree	1	16.7
Strongly agree	1	16.7
Completely agree	4	66.7

Pressure measurements at home reduced my worries about unidentified high ocular pressure...

Answer	Frequency (N=6)	
	n	%
Indifferent	1	16.7
Strongly agree	2	33.3
Completely agree	3	50.0

Pressure measurements at home increased my motivation to regularly take my pressure lowering medication...

Answer	Frequency (N=6)	
	n	%
Somewhat disagree	1	16.7
Indifferent	2	33.3
Strongly agree	1	16.7
Completely agree	1	16.7
Missing	1	16.7

 Implantata Ophthalmic Products GmbH	Clinical Investigation Report ARGOS-KP01	Revision A Page 77 of 114
--	---	----------------------------------

4.8 Safety

4.8.1 Adverse Events

Information about all untoward medical occurrences occurring during a subject's study participation was collected at study visits through examination by the Investigator. Information about events occurring between visits was obtained by asking the patient non-leading questions.

Particular attention was paid to ophthalmic AEs, for which increased risks are considered possible (CIP 7.4 Risks and anticipated adverse device effects to be assed):

- Retroprosthetic membrane formation
- Increased intraocular pressure
- Glaucoma progression
- Endophthalmitis
- Angle narrowing or angle closure
- Sterile keratolysis
- Fungal infections
- Choroidal effusions/hemorrhage
- Vitritis
- Vitreous hemorrhage
- Retina detachments
- Corneal melt/necrosis
- Loss of implant, disintegration of implant, implant dislocation or extrusion
- Need for GDD implantation (pars plana vitrectomy)
- Cystoid macular edema
- Fibrin reactions
- Hypopyons
- Pigment dispersion during surgery
- Postsurgical pigment dispersion

Overall 168 AEs were reported during the ARGOS-KP01 study. 12 months after implantation were reported 168 AEs in 13 patients, including 23 SAEs in 9 patients. 92 AEs in 5 patients were rated as unlikely to the medical device and 61 AEs in patients have no relationship to the ARGOS-IO sensor. Only 15 AEs in four patients were possible related to the medical device: anterior chamber cell,

 Implantata Ophthalmic Products GmbH	Clinical Investigation Report ARGOS-KP01	Revision A Page 78 of 114
--	---	----------------------------------

cystoid macular edema, hypotony of the eye, iris adhesion, pigment dispersion, vitritis, increased intraocular pressure and retroprosthetic membrane.

Table 9 lists all adverse events including SAEs.

Table 9: Summary of all AEs

Adverse Events	n	%	Total (N=13)
Any System Organ Class	13	100	168
Ear and Labyrinth Disorders	1	7.7	
Tinnitus	1	7.7	
Eye Disorders	11	84.6	79
Eye pain	6	46.2	7
Hypotony of eye	6	46.2	8
Vitritis	4	30.8	5
Cystoid macular edema	3	23.1	7
Retinal detachment	3	23.1	3
Choroidal detachment	2	15.4	2
Corneal infiltrates	2	15.4	2
Iris adhesion	2	15.4	4
Keratitis	2	15.4	3
Retinopathy proliferative	2	15.4	4
Visual acuity reduced	2	15.4	2
Anterior chamber cell	1	7.7	1
Anterior chamber fibrin	1	7.7	1
Blepharitis	1	7.7	1
Choroidal haemorrhage	1	7.7	1
Conjunctival disorder	1	7.7	1
Conjunctival haemorrhage	1	7.7	1
Conjunctival hyperaemia	1	7.7	1
Corneal epithelium defect	1	7.7	3
Corneal neovascularisation	1	7.7	1
Corneal perforation	1	7.7	1
Erythema of eyelid	1	7.7	1
Eye inflammation	1	7.7	1
Eye pruritus	1	7.7	1
Keratic precipitates	1	7.7	1
Lacrimation increased	1	7.7	1
Lens disorder	1	7.7	1
Ocular discomfort	1	7.7	2
Pigment dispersion	1	7.7	1
Retinal disorder	1	7.7	1
Retinal haemorrhage	1	7.7	1
Retinal scar	1	7.7	1
Retinal tear	1	7.7	1

 Implantata Ophthalmic Products GmbH	Clinical Investigation Report ARGOS-KP01	Revision A
		Page 79 of 114

Retinal thickening	1	7.7	1
Subretinal fibrosis	1	7.7	1
Trichiasis	1	7.7	2
Visual impairment	1	7.7	1
Vitreous haemorrhage	1	7.7	1
Vitreous opacities	1	7.7	1
Gastrointestinal Disorders	2	15.4	2
Constipation	1	7.7	1
Nausea	1	7.7	1
General Disorders and Administration Site Conditions	3	23.1	4
Atrophy of the donor cornea	1	7.7	1
Leakage between keratoprosthesis and keratoplasty	1	7.7	1
Subjectively worse impression	1	7.7	1
Drug intolerance	1	7.7	1
Infections and Infestations	3	23.1	3
Bacterial disease carrier	1	7.7	1
Gastroenteritis	1	7.7	1
Urinary tract infection	1	7.7	1
Injury, Poisoning and Procedural Complications	4	30.8	8
Procedural Pain	3	23.1	3
Hyphaema	1	7.7	1
Post procedural complication	1	7.7	1
Post procedural haemorrhage	1	7.7	1
Suture related complication	1	7.7	1
Corneal graft melt	1	7.7	1
Investigations	8	61.5	35
Intraocular pressure increased	8	61.5	30
Intraocular pressure decreased	3	23.1	4
Seidel Test positive	1	7.7	1
Musculoskeletal and Connective Tissue Disorders	1	7.7	3
Back pain	1	7.7	1
Bone pain	1	7.7	1
Fibromyalgia	1	7.7	1
Nervous System Disorders	3	23.1	4
Dizziness	1	7.7	1
Headache	1	7.7	1
Paraesthesia	1	7.7	1
Syncope	1	7.7	1
Product Issues	8	61.5	13
Retroprosthetic membrane	6	46.2	7
Device material opacification (BkPro and IOL)*	3	23.1	5
Dislocation of ARGOS-IO sensor	1	7.7	1

 Implandata Ophthalmic Products GmbH	Clinical Investigation Report ARGOS-KP01	Revision A Page 80 of 114
--	---	------------------------------

Psychiatric Disorders	1	7.7	1
Panic attack	1	7.7	1
Renal and Urinary Disorders	1	7.7	2
Renal failure	1	7.7	2
Surgical and Medical Procedures	6	46.2	12
Corneal sutures removal	5	38.5	8
Corneal transplant	2	15.4	4
Vascular Disorders	1	7.7	1
Hypertension	1	7.7	1
Source: Final Statistical Output – Tables			
Table 14.3.1.3 – Adverse Events by SOC and PT: first 4 weeks, 16 weeks, 28 weeks, 12 months following implantation surgery			
%: Percentage based on N			
N: Number of subjects in total (Safety Set)			
n: Number of patients reporting at least one adverse event with the specification			
*: 3x opacification of BkPro's rear surface/1x milky optic of KPro/1x hazy IOL			

The majority of the AEs (116 of 168) has a relationship to the medical procedure which implements both the implantation of the ARGOS-IO sensor and the Boston-Keratoprosthesis surgery (Table 10). Often, an AE cannot be assigned definitely to one procedure as the two implantations were performed in one surgery and many of the AEs are already known as complications for a stand-alone BkPro procedure.

 Implantata Ophthalmic Products GmbH	Clinical Investigation Report ARGOS-KP01	Revision A
		Page 81 of 114

Table 10: AEs related to the Medical Procedure – Time of Occurrence and Outcome

Adverse Event	Total (N=13)												Outcome
	First 4 weeks			First 16 weeks			First 28 weeks			First 12 months			
	n	%	AE	n	%	AE	n	%	AE	n	%	AE	
Any System Organ Class	5	38.5	32	10	76.9	62	13	100	80	13	100	116	
Eye Disorders	9	69.2	16	11	84.6	36	11	84.6	44	11	84.6	61	
Hypotony of eye	1	7.7	2	4	30.8	5	5	38.5	6	6	46.2	7	6 recovered 1 recovering
Eye Pain	2	15.4	2	3	23.1	3	3	23.1	4	4	30.8	5	recovered
Cystoid macular edema	0	0.0	0	2	15.4	3	3	23.1	4	3	23.1	6	4 recovered 1 recovering 1 recurrent
Vitritis	0	0.0	0	1	7.7	1	1	7.7	1	3	23.1	4	recovered
Choroidal detachment	0	0.0	0	2	15.4	2	2	15.4	2	2	15.4	2	recovered
Corneal infiltrates	0	0.0	0	0	0.0	0	1	7.7	1	2	15.4	2	1 recovered 1 recovered with sequelae
Retinal detachment	0	0.0	0	1	7.7	1	1	7.7	1	2	15.4	2	1 recovered 1 recovered with sequelae
Retinopathy proliferative	0	0.0	0	1	7.7	2	1	7.7	2	2	15.4	4	recovered
Visual acuity reduced	0	0.0	0	2	15.4	2	2	15.4	2	2	15.4	2	1 recovered 1 recovering
Anterior chamber cell	1	7.7	1	1	7.7	1	1	7.7	1	1	7.7	1	recovered
Anterior chamber fibrin	1	7.7	1	1	7.7	1	1	7.7	1	1	7.7	1	recovered
Blepharitis	1	7.7	1	1	7.7	1	1	7.7	1	1	7.7	1	recovering

IOP Implandata Ophthalmic Products GmbH	Clinical Investigation Report ARGOS-KP01									Revision A	
										Page 82 of 114	

Choroidal haemorrhage	0	0.0	0	0	0.0	0	0	0.0	0	1	7.7	1	not recovered
Conjunctival disorder	1	7.7	1	1	7.7	1	1	7.7	1	1	7.7	1	recovered
Conjunctival haemorrhage	1	7.7	1	1	7.7	1	1	7.7	1	1	7.7	1	recovered
Conjunctival hyperaemia	0	0.0	0	0	0.0	0	0	0.0	0	1	7.7	1	recovering
Corneal epithelium defect	0	0.0	0	0	0.0	0	0	0.0	0	1	7.7	1	recovered
Corneal neovascularisation	0	0.0	0	0	0.0	0	1	7.7	1	1	7.7	1	not recovered
Eye inflammation	0	0.0	0	0	0.0	0	0	0.0	0	1	7.7	1	recovered
Eye pruritus	1	7.7	1	1	7.7	1	1	7.7	1	1	7.7	1	recovered
Iris adhesion	0	0.0	0	1	7.7	1	1	7.7	2	1	7.7	2	recovered
Keratic precipitates	0	0.0	0	0	0.0	0	0	0.0	0	1	7.7	1	recovered
Keratitis	0	0.0	0	1	7.7	1	1	7.7	1	1	7.7	1	recovered
Lacrimation increased	1	7.7	1	1	7.7	1	1	7.7	1	1	7.7	1	recovered
Capsular bag instability	1	7.7	1	1	7.7	1	1	7.7	1	1	7.7	1	unknown
Ocular discomfort	1	7.7	1	1	7.7	1	1	7.7	2	1	7.7	2	recovered
Pigment dispersion	1	7.7	1	1	7.7	1	1	7.7	1	1	7.7	1	recovered
Retinal disorder	0	0.0	0	1	7.7	1	1	7.7	1	1	7.7	1	recovered
Retinal haemorrhage	0	0.0	0	0	0.0	0	0	0.0	0	1	7.7	1	recovered
Retinal scar	0	0.0	0	1	7.7	1	1	7.7	1	1	7.7	1	recovered
Retinal tear	1	7.7	1	1	7.7	1	1	7.7	1	1	7.7	1	recovered
Retinal thickening	0	0.0	0	1	7.7	1	1	7.7	1	1	7.7	1	not recovered
Vitreous haemorrhage	1	7.7	1	1	7.7	1	1	7.7	1	1	7.7	1	recovered
Vitreous opacities	0	0.0	0	0	0.0	0	1	7.7	1	1	7.7	1	recovered
General Disorder and Administration	0	0.0	0	0	0.0	0	1	7.7	1	2	15.4	2	
Site Conditions													
Atrophy of the donor cornea	0	0.0	0	0	0.0	0	1	7.7	1	1	7.7	1	not recovered
Subjectively worse impression	0	0.0	0	0	0.0	0	0	0.0	0	1	7.7	1	recovered
Injury, Poisoning and Procedural Complications	4	30.8	6	4	30.8	7	4	30.8	7	4	30.8	7	
Procedural pain	3	23.1	3	3	23.1	3	3	23.1	3	3	23.1	3	recovered
Hyphaema	1	7.7	1	1	7.7	1	1	7.7	1	1	7.7	1	recovered
Post procedural complication	1	7.7	1	1	7.7	1	1	7.7	1	1	7.7	1	recovered
Post procedural haemorrhage	1	7.7	1	1	7.7	1	1	7.7	1	1	7.7	1	recovered

 Implantata Ophthalmic Products GmbH	Clinical Investigation Report ARGOS-KP01	Revision A
		Page 83 of 114

Suture related complication	0	0.0	0	1	7.7	1	1	7.7	1	1	7.7	1	recovered
Investigations	6	46.2	7	6	46.2	10	7	53.8	16	7	53.8	25	
Intraocular pressure increased	6	46.2	7	6	46.2	10	7	53.8	16	7	53.8	24	recovered
Intraocular pressure decreased	0	0.0	0	0	0.0	0	0	0.0	0	1	7.7	1	not recovered
Nervous System Disorders	1	7.7	1	1	7.7	1	1	7.7	1	1	7.7	1	
Headache	1	7.7	1	1	7.7	1	1	7.7	1	1	7.7	1	recovered
Product Issue	1	7.7	1	5	38.5	6	6	46.2	7	7	53.8	11	
Retroprosthetic membrane	1	7.7	1	4	30.8	4	4	30.8	4	5	38.5	5	3 recovered
Device material opacification (BKPro and IOL)*	0	0.0	0	2	15.4	2	2	15.4	2	3	23.1	5	2 not recovered
Dislocation of ARGOS-IO sensor	0	0.0	0	1	7.7	1	1	7.7	1	1	7.7	1	recovered
Surgical and Medical Procedures	1	7.7	1	2	15.4	2	3	23.1	4	6	46.2	9	
Corneal suture removal	1	7.7	1	1	7.7	1	2	15.4	2	5	38.5	7	recovered
Corneal graft melt	0	0.0	0	1	7.7	1	1	7.7	2	1	7.7	2	recovered

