Table 11: ADEs – Time of Occurrence and Outcome

Adverse Device Defect	Total (N=13)												Outcome
	First 4 weeks			First 16 weeks			First 28 weeks			First 12 months			
	n	%	AE	n	%	AE	n	%	AE	n	%	AE	
Any System Organ Class	1	7.7	3	3	23.1	8	4	30.8	11	4	30.8	15	
Eye Disorders	2	15.4	2	4	30.8	6	4	30.8	9	4	30.8	13	
Cystoid macular edema	0	0.0	0	2	15.4	3	3	23.1	4	3	23.1	6	4 recovered 1 recovering 1 recurrent
Hypotony of eye	0	0.0	0	0	0.0	0	1	7.7	1	2	15.4	2	recovered
Anterior chamber cell	1	7.7	1	1	7.7	1	1	7.7	1	1	7.7	1	recovered
Iris adhesion	0	0.0	0	1	7.7	1	1	7.7	2	1	7.7	2	recovered
Pigment dispersion	1	7.7	1	1	7.7	1	1	7.7	1	1	7.7	1	recovered
Vitritis	0	0.0	0	0	0.0	0	0	0.0	0	1	7.7	1	recovered
Investigations	1	7.7	1	1	7.7	1	1	7.7	1	1	7.7	1	
Intraocular pressure increased	1	7.7	1	1	7.7	1	1	7.7	1	1	7.7	1	recovered
Product Issue	0	0.0	0	1	7.7	1	1	7.7	1	1	7.7	1	
Retroprosthetic membrane	0	0.0	0	1	7.7	1	1	7.7	1	1	7.7	1	not recovered

Source: Final Statistical Output – Tables

Table 14.3.1.6 – Adverse Device Effects by SOC and PT – periods first 4 weeks, 16 weeks, 28 weeks, 12 months following implantation surgery

#: Percentage based on N

N: Number of subjects in total (Safety Set)

n: Number of patients reporting at least one adverse event with the specification

AE: Number of individual adverse events which occurred among the n patients

 Implantata Ophthalmic Products GmbH	Clinical Investigation Report ARGOS-KP01	Revision A Page 86 of 114
--	---	----------------------------------

Of the 15 ADEs, three were classified as mild, six as moderate and six as severe.

- Anterior chamber cell: moderate
 - Inflammation is a normal and common response to any trauma of the eye, including intraocular surgery. A moderate intraocular inflammation after surgery is expected and can be caused by the implantation of the Boston keratoprosthesis as well as by the manipulation of the iris caused by the implantation of the ARGOS-IO sensor. A self-resolving, sterile anterior chamber inflammation after surgery is not expected to negatively impact device functioning, healing or functional recovery.
- Cystoid macular edema: 3 moderate, 3 severe
 - A cystoid macular edema is a known complication of all intraocular surgeries and has in most times a self-limiting nature. In stand-alone BK-Pro surgery, CME is with up to 27% also a frequent complication (Moshin H. Ali, 2018). However, a causal relationship with the ARGOS-IO sensor can never be excluded.

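### Tables 10 and 11 print four impossible early patient counts: the overall row is below Eye Disorders at 4 and 16 weeks

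*Protocol*

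**What the plan says.** The figures are in section 4.8.1 of the clinical investigation report (the file supplied as the protocol). Each period has three columns: patients, percent and events, with N = 13.

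- **Table 10, overall row, 4 and 16 weeks:** "Any System Organ Class 5 38.5 32 10 76.9 62".
- **Table 10, Eye Disorders, same periods:** "Eye Disorders 9 69.2 16 11 84.6 36".
- **Table 10, Investigations, 4 weeks:** "Investigations 6 46.2 7", with the term row beneath it "Intraocular pressure increased 6 46.2 7".
- **Table 11, overall row, 4 and 16 weeks:** "Any System Organ Class 1 7.7 3 3 23.1 8". Eye Disorders in the same table shows 2 patients at 4 weeks and 4 at 16 weeks.
- **Table 10, Product Issue, 4, 16 and 28 weeks:** "Product Issue 1 7.7 1 5 38.5 6 6 46.2 7".
- **Table 10, all four periods, under Surgical and Medical Procedures:** "Corneal graft melt 0 0.0 0 1 7.7 1 1 7.7 2 1 7.7 2". Table 9, which covers all AEs, has "Corneal graft melt 1 7.7 1" under Injury, Poisoning and Procedural Complications.

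The footnotes to Tables 9 and 11 define n as patients reporting at least one event of the kind named. SAP section 10.2 counts a patient once per system organ class (SOC), requires the number of patients with at least one AE to be shown, and makes the periods cumulative from surgery.

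**The concern.** A patient with an eye disorder is also a patient with an event in some SOC. The overall count must therefore be at least as large as every SOC count in its column, and every SOC count at least as large as each of its terms. Table 10 breaks this rule at 4 and 16 weeks, and so does Table 11.

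Incidence of AEs and adverse device events in the first 4 and 16 weeks is a stated secondary safety endpoint. Table 11 is the device-effect part of it, and SAP section 10.2 tabulates procedure-related AEs under the same heading. As printed, a reader cannot tell which early incidence to use.

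**Working it through.** **1. Do the printed figures reproduce?** Percentages are n/13: 5/13 = 38.5%, 9/13 = 69.2%, 10/13 = 76.9%, 11/13 = 84.6%; in Table 11, 1/13 = 7.7%, 2/13 = 15.4%, 3/13 = 23.1%, 4/13 = 30.8%. All eight match.

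Event totals also re-add. Table 10, by SOC in printed order:
- 4 weeks: 16+0+6+7+1+1+1 = 32
- 16 weeks: 36+0+7+10+1+6+2 = 62
- 28 weeks: 44+1+7+16+1+7+4 = 80
- 12 months: 61+2+7+25+1+11+9 = 116

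Table 11: 2+1+0 = 3; 6+1+1 = 8; 9+1+1 = 11; 13+1+1 = 15. A digit damaged in PDF extraction would not keep its matching percentage, so extraction does not explain the patient counts.

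**2. Overall n against the largest SOC n.**

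| Table, period | Overall n | Eye Disorders n | Largest other SOC n | Consistent? |
|---|---|---|---|---|
| 10, 4 weeks | 5 | 9 | 6 | No |
| 10, 16 weeks | 10 | 11 | 6 | No |
| 10, 28 weeks | 13 | 11 | 7 | Yes |
| 10, 12 months | 13 | 11 | 7 | Yes |
| 11, 4 weeks | 1 | 2 | 1 | No |
| 11, 16 weeks | 3 | 4 | 1 | No |
| 11, 28 weeks | 4 | 4 | 1 | Yes |
| 11, 12 months | 4 | 4 | 1 | Yes |

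**3. Which row is wrong?** An SOC count must lie between its largest term count and the sum of its term counts.

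- *Table 10, 4 weeks.* Investigations and its term for raised intraocular pressure both show 6. No change to Eye Disorders can make an overall count of 5 possible.
- *Table 10, 16 weeks.* The Eye Disorders terms allow anything from 4 upwards. An integer feasibility check (13 patients, all term and SOC rows, the 16-week Product Issue patient count left free) accepts both 10 in both rows and 11 in both rows.
- *Table 11, 4 weeks.* The Eye Disorders terms are anterior chamber cell (1) and pigment dispersion (1), so 1 or 2 patients.
- *Table 11, 16 weeks.* The terms allow 2 to 5 patients. In both Table 11 cells, correcting either row gives a possible table.

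**4. Size.** The 95% Clopper-Pearson limits for x of 13 are the 0.025 quantile of Beta(x, 14−x) and the 0.975 quantile of Beta(x+1, 13−x).

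| Cell | As printed | If Eye Disorders is right |
|---|---|---|
| Table 10, 4 weeks | 5/13 = 38.5% (13.9–68.4) | at least 9/13 = 69.2% (38.6–90.9) |
| Table 10, 16 weeks | 10/13 = 76.9% (46.2–95.0) | at least 11/13 = 84.6% (54.6–98.1) |
| Table 11, 4 weeks | 1/13 = 7.7% (0.2–36.0) | at least 2/13 = 15.4% (1.9–45.4) |
| Table 11, 16 weeks | 3/13 = 23.1% (5.0–53.8) | 4/13 = 30.8% (9.1–61.4) |

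The last entry is exactly 4, because the cumulative overall count is 4 at 28 weeks. For Table 10 at 4 weeks, Investigations alone gives at least 6/13 = 46.2% (19.2–74.9). If instead the overall row is right in the other three cells, Eye Disorders is at most 10, 1 and 3.

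**5. Product Issue, Table 10.** Term events at 4, 16, 28 weeks and 12 months sum to 1, 4+2+1 = 7, 4+2+1 = 7 and 5+5+1 = 11. The SOC row prints 1, 6, 7, 11. All three term rows are identical at 16 and 28 weeks, so with cumulative counting the same patients are in each. The SOC row nevertheless moves from 5 to 6 patients and from 6 to 7 events.

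**6. Corneal graft melt.** Table 10 has 2 procedure-related events by 12 months; Table 9 has 1 event under that name among all AEs. A subset cannot exceed its total, so the label or a count is wrong.

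**The case against.** The strongest counter-argument is that these are slips in descriptive in-text tables. The SAP's counting rules are sound, no tests are planned, no visible interval uses these counts, and the report's safety summary rests on 12-month totals. That limits the consequence but does not remove the contradiction.

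Four narrower points deserve an answer.

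- **Table 10 at 4 weeks is inference, not proof.** It assumes that the Investigations rows are right. That is fair, but otherwise Eye Disorders, Investigations and its term would all have to be wrong together.
- **Procedure-related AEs are not named in the endpoint wording.** This is correct. Strictly within the endpoint, the conflict is the two Table 11 cells, one patient each. SAP section 10.2 nevertheless plans procedure-related counts at 4 and 16 weeks, with intervals, under the secondary safety endpoints.
- **Product Issue may be a slip in a term row, or extraction damage.** The printed total of 62 needs Product Issue to be 6; with 7 it would be 63. This favours a term slip without settling it. The outcome column in that block does look misaligned. The patient counts, however, carry matching percentages (5 = 38.5%, 6 = 46.2%) and still conflict with unchanged term rows.
- **Graft melt may be only a mislabel.** This is plausible. Table 9 lists corneal transplant (2 patients, 4 events) in the SOC where Table 10 puts graft melt. Table 10's Injury block sums to 7 events without graft melt, against 8 in Table 9 with it. A label error would still need correcting.

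**Conclusion.** The concern holds. In four cells the overall and Eye Disorders rows cannot both be right, given n as patients with at least one event and cumulative periods. The footnote defining n was read from Tables 9 and 11; SAP section 10.2 gives the same rule for Table 10.

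For Table 10 at 4 weeks the overall figure is too low by at least one patient of 13 if Investigations is right, and by at least four if Eye Disorders is right. In the other three cells the direction is unknown: either the overall row is too low or Eye Disorders is too high, by at least one patient. The Product Issue and graft melt entries in Table 10 are separate inconsistencies whose wrong side is also not established.

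The 12-month primary safety endpoint and the 28-week and 12-month overall patient counts are not shown to be affected. The source tables were not available and may be correct. The matter should be put right because these are reported early safety incidences.

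**What to change.** - Compare Table 10 with source Table 14.3.1.7, Table 11 with Table 14.3.1.6, and both with the AE listing (16.2.7.1). Correct whichever rows are wrong, without presuming that it is the overall row except as a first suspicion for Table 10 at 4 weeks.
- Re-run the source tables only if they carry the same fault.
- In the same pass, reconcile the Product Issue rows (and the 16-week event total of 62, if the SOC row changes), and settle the graft melt label and count against Table 14.3.1.3.
- Check the 4- and 16-week percentages and Clopper-Pearson intervals in Table 14.3.1.2 against the corrected counts.
- Before reissue, apply two checks to all AE tables: overall n ≥ SOC n ≥ term n, and no subset above its all-AE total.

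The cost is low: a check of two in-text tables against existing output, and corrected report pages. No new data are needed.
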